108 awareness of HIV status, reduce injection-related and same-sex risk behavior, improve health,

109 reduce mortality, and decrease the infectiousness of HIV-infected persons in the community
110 through effective viral suppression. We will evaluate the community-level effectiveness of
111 MSM//PWID-focused integrated care centers (ICCs), which will provide core and group-specific
112 HIV prevention and treatment services at a single venue utilizing a cluster-randomized trial
113 design in 22 sites across India.

114

115 Our hypotheses are:

116 1) Establishing ICCs will increase access to HCT and knowledge of HIV status among MSM and
117 PWID.

118 2) In the subset of HIV-infected MSM and PWID, ICCs will increase access to care, use of ART
119 and will decrease community viral load.

120 3) Establishing ICCs will decrease transmission risk behaviors and HIV incidence among MSM
121 and PWID via improved access to prevention services (NSEP, OAT, IEC).

122

123 **METHODS/ DESIGN**

124 **Study design**

125 The study design is a cluster-randomized trial with parallel MSM and PWID strata. ICCs
126 were scaled-up and implemented at sites allocated to the intervention arm, and outcomes will be
127 assessed by pre- and post-intervention surveys at intervention and control sites (**Figure 1**). As
128 MSM and PWID are hidden populations with no sampling frame, respondent-driven sampling
129 (RDS) will be used to accrue samples for the two independent cross-sectional surveys. Sites (10
130 MSM and 12 PWID sites) were randomized in a 1:1 allocation ratio. The trial is currently
131 underway. The pre-intervention survey took place between September 2012 and December 2013;

132 the ICCs were scaled up between June 2014 and February 2015. Post-intervention survey
133 commenced in August 2016 and is expected to be complete by April 2017.

134 **Study sites**

135 Twenty-seven candidate sites were selected (15 PWID, 12 MSM; **Figure 2**) of which 22
136 were included in the trial. Sites were selected to represent regions of India where there was
137 preliminary evidence of high HIV prevalence or high risk of HIV acquisition through discussions
138 with the Targeted Interventions (TI) Division of NACO, India. We ensured sufficient distance
139 between sites to minimize potential overlap (contamination) between intervention and control
140 sites. MSM sites were selected to represent cities with established HIV epidemics among MSM,

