141 smaller cities in high prevalence states and cities with anecdotal reports of HIV among MSM but
142 no published reports [1]. PWID sites were selected to represent varying stages of drug use
143 epidemics (established drug use epidemics, large metropolitan cities, cities with documented
144 emerging drug use epidemics and cities with anecdotal evidence of emerging drug use) [1].

145 **Design of the intervention**

146 The intervention is vertically integrated delivery of HIV prevention and treatment
147 services in stand-alone venues – called ICCs -- to disenfranchised high-risk groups. These
148 centers will provide services critical to HIV prevention and essential outpatient services for HIV-
149 infected persons. The core services at MSM ICCs are: HCT, condom promotion and distribution,
150 diagnosis and treatment of STIs, testing services for spouses, HIV and risk reduction counseling
151 services as well as counseling for substance use and depression. In addition, PWID ICCs will
152 also include NSEP and OAT (using medically managed buprenorphine). Finally, in both PWID
153 and MSM ICCs, we established linkages with local government centers to deliver treatment for
154 HIV (ART) and tuberculosis. All ICC services are currently available in India but are typically

155 provided by independent and insulated service organizations. The keystone of the ICC
156 intervention is vertically integrated service delivery to disenfranchised high-risk groups.

157 ICCs are based on the premise that interventions that combine approaches and address
158 multiple levels (e.g., community-, network-, and individual-levels) can lead to sustainable
159 change [37-42]. At the core of our model is a structural intervention that seeks to bring about
160 *community-level* change through provision of integrated services in a non-discriminatory setting
161 with nested approaches guided by social and behavioral science theories to induce behavioral
162 change at *network* and *individual* levels. The structural change (i.e., establishment of ICCs) is
163 based on the Andersen and Aday model of health care utilization [43, 44]. The goal is to address
164 environmental, predisposing, enabling, and need factors in MSM and PWID that promote or
165 inhibit health services use. To implement this structural change, we rely on the diffusion of
166 innovations [45] and ‘tipping point’ theories [46]. We propose to leverage MSM and PWID

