444 individual-level analyses using multi-level random effects regression approaches (Stata
445 GLLAMMs program) to account for dependence of responses within clusters [54-56]. These
446 models allow inclusion of fixed effects (e.g., intervention), random effects (e.g., clusters),
447 adjustment for pre-intervention covariates at the individual and cluster level, and incorporation
448 of scaled RDS weights as sampling weights. Finally, we will conduct descriptive analyses of the
449 HIV care continuum, before and after the intervention phase of the study, in which completion of
450 earlier steps are assumed to be necessary to complete later steps. Additionally, we will consider
451 sensitivity analyses of outcomes in the HIV care continuum, where biologic markers such as

452 HIV RNA and serum antiretroviral drug testing, are used to supplement self-reported data on
453 access to care.

454 Several subgroup analyses are also planned. First, we will analyze all outcomes
455 separately within each stratum (PWID and MSM). Using the combined sample of MSM and
456 PWID sites, we will further compare all outcomes within subgroups defined by age, marital
457 status, educational attainment, substance use (drug and alcohol use), and personal network size
458 (number of persons in risk group [PWID or MSM] known and seen in the prior 30 days). Using
459 only the PWID sites, we will also analyze subgroup differences by age, sex, marital status,
460 educational attainment, substance use (including alcohol use), personal network size and region.
461 In the MSM sites, we will also analyze subgroup differences by age, sexual identity, marital
462 status, educational attainment, substance use (including alcohol use), personal network size and
463 region. We also plan subgroup analyses by HIV serostatus and awareness of status for risk
464 behaviors, HIV testing of spouses, substance use, stigma, and depression.

465

466 *Network- and individual-levels.*

467 Network effects will be ascertained by comparing utilization of ICCs and services within
468 ICCs across networks as defined by RDS. For example, we will examine utilization patterns
469 across recruiters and recruits in the evaluation RDS. We will also ascertain whether utilization of
470 ICCs varied by wave of RDS. Individual-level comparisons will draw on data from post-
471 intervention RDS participants in the intervention clusters, in which extra questions will address

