Awareness of HIV status, access to care, and HIV treatment				
2	Awareness of HIV status among HIV-seropositive persons	1. Survey 2. Serologic HIV test	HIV seropositive participants	Reports having a positive HIV test OR being told by a doctor that he/she had HIV.
3	Accessing HIV medical care in prior 6 months	1. Survey 2. Serologic HIV test	HIV seropositive participants	Reports seeing a doctor about HIV AND reports visit with the indicated doctor in the prior 6 months.
4	Use of ART among ART-eligible	1. Survey 2. Serologic HIV test	HIV seropositive participants who meet either criteria 1 or 2 1. Reports taking ART at any time in the past OR 2. CD4 <350 cells/ μ L	Reports ART use in prior 30 days.
5	Use of trimethoprim-sulfamethoxazole (TMP-SMX) when indicated	1. Survey 2. Serologic HIV test 3. CD4	HIV seropositive AND CD4 count < 200 cells/ μ L	Reports taking TMP-SMX in past 30 days
6	Viral suppression among ART-eligible	1. Survey 2. Serologic HIV test 3. CD4 4. HIV RNA	HIV seropositive participants who meet either criteria 1 or 2 1. Reports taking ART at any time in the past OR 2. CD4 <350 cells/ μ L	HIV RNA <150c/mL
7	Viral suppression among HIV-positive	1. Serologic HIV test 2. HIV RNA	HIV seropositive participants	HIV RNA <150c/mL
8	Average CD4 cell count among HIV-positive	1. Serologic HIV test 2. CD4 cell count	HIV seropositive participants	CD4 cell count

Table 1. Outcome definitions for the Indian National Collaboration on AIDS (NCA) study

	Outcome	Data inputs	Population (denominator)	Definition
Risk behaviors, substance use, and depression				
9	Unprotected anal intercourse with non-main male partner in prior 6 months [MSM]	Survey	Participants at MSM sites	Does not report “always” using a condom during insertive or receptive anal sex with non-main (e.g., casual, one-time partner, sex worker) male partners in the prior 6 months
10	Number of non-main male sexual partners in prior 6 months [MSM]	Survey	Participants at MSM sites	Number of non-main male (e.g., casual, one-time partner, sex worker) male partners with whom the participant reports having insertive or receptive anal sex in the prior 6 months
11	Symptoms of sexually transmitted infection [MSM]	Survey	Participants at MSM sites	Reports genital/anal discharge, pain, or ulcer in prior 6 months
12	Syphilis infection	1. RPR test 2. TPHA test	Participants at MSM sites	Positive for syphilis infection by both RPR and TPHA tests

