13	Shared injection equipment in prior 6 months [PWID]	Survey	Participants at PWID sites	Reports sharing (passing or receiving) a needle and/or syringe with another individual in the prior 6 months
14	Shared injection equipment at last use among active injectors [PWID]	Survey	Participants at PWID sites that report injection of one or more drugs in prior 6 months	Reports sharing (passing or receiving) a needle and/or syringe with another individual at last injection
15	Reported injection abstinence in prior 6 months [PWID]	Survey	Participants at PWID sites	Denies injecting any drug in prior 6 months
16	Hazardous alcohol use or dependence	Survey	All participants	Score ≥ 8 (hazardous) or ≥ 15 on Alcohol Use Disorder Identification Test (AUDIT)[61]
17	Depression	Survey	All participants	Score ≥ 10 on Patient Health Questionnaire (PHQ)-9[62]

Table 1. Outcome definitions for the Indian National Collaboration on AIDS (NCA) study

	Outcome	Data inputs	Population (denominator)	Definition
Services and stigma				
18	Spouse HIV testing among married participants	Survey	Participants who report being married	Reports spouse has ever been tested for HIV
19	Symptoms of sexually transmitted infection for which participant sought care in prior 6 months [MSM]	Survey	Participants at MSM sites	Reports genital/anal discharge, pain, or ulcer in prior 6 months AND reports seeking medical care for symptom(s)
20	Used needle/syringe exchange program (NSEP) in prior 6 months [PWID]	Survey	Participants at PWID sites	Reports NSEP use in prior 6 months
21	Used needle/syringe exchange program (NSEP) in prior 6 months among active injectors [PWID]	Survey	Participants at PWID sites that report injection of one or more drugs in prior 6 months	Reports NSEP use in prior 6 months
22	Used opioid agonist therapy (OAT) in prior 6 months [PWID]	Survey	Participants at PWID sites	Reports OAT in prior 6 months
23	Stigma subtypes	Survey	All participants	Summed score from each of four 6-item stigma scales (enacted, vicarious, felt normative, and internalized stigma)[63]
Community viral load and HIV incidence				
24	Prevalence of viremic individuals in population	1. Serologic HIV test 2. HIV RNA	All participants	Prevalence of HIV-positive subjects with HIV RNA >150c/mL[64]
25	Average viral load in HIV-positive participants	1. Serologic HIV test 2. HIV RNA	HIV seropositive participants	Average (log ₁₀) HIV RNA

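### Intervention-versus-control contrasts within subgroups defined by awareness of HIV status or substance use, both of which ICCs are meant to change, can differ through subgroup composition alone

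*Combined protocol and SAP*

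**What the plan says.** The subgroup paragraph is in the Analysis plan under Community level, where the main analysis compares intervention with control cities. It contains two relevant plans.

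- **Substance use.** For the combined sample: "PWID sites, we will further compare all outcomes within subgroups defined by age, marital", continuing "status, educational attainment, substance use (drug and alcohol use), and personal network size". Substance use is listed again for the PWID sites and for the MSM sites. No time window is given.
- **Awareness.** The paragraph ends: "region. We also plan subgroup analyses by HIV serostatus and awareness of status for risk", continuing "behaviors, HIV testing of spouses, substance use, stigma, and depression".

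Elsewhere the documents treat both factors as things the intervention should move.

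- Study aims and hypotheses, hypothesis 1: "1) Establishing ICCs will increase access to HCT and knowledge of HIV status among MSM and" PWID. Table 1 makes awareness secondary outcome 2: "Awareness of HIV status among HIV-seropositive persons".
- Design of the intervention lists, among core ICC services, "services as well as counseling for substance use and depression. In addition, PWID ICCs will" add needle exchange and opioid agonist therapy.
- Table 1 makes injection abstinence secondary outcome 15 ("Denies injecting any drug in prior 6 months") and hazardous alcohol use secondary outcome 16.

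Study design describes the pre- and post-intervention surveys as independent cross-sections. The post-intervention survey starts about 24 months after the ICCs were set up. The plan does not limit the subgroup factors to pre-intervention values and does not call these subgroup analyses descriptive.

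**The concern.** Randomisation makes the cities comparable as wholes. It does not make comparable the people within a city who are sorted by something the intervention has changed. If ICCs raise awareness, the aware group in intervention cities includes newly diagnosed people whose counterparts in control cities are counted as unaware. If ICCs reduce substance use, the remaining users in intervention cities are a different selection from the users in control cities. An arm contrast within either subgroup then mixes any real effect with a change in who is in the subgroup.

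The outcomes exposed are risk behaviours, spouse testing, substance use, stigma and depression (by awareness) and all outcomes, including HIV testing in the prior 12 months (by substance use). Under Dissemination, stakeholders may adopt only parts of the ICC model. A false signal among aware people or among substance users could bear on that choice, and more success in raising awareness makes the distortion larger.

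**Working it through.** **Check of inputs against the plan's own figure.** The documents state no figure for the subgroup analyses. The nearest is in Statistical power: 80% power with 11 + 11 clusters, 42% vs 30%, k = 0.25, and 1000 per cluster with RDS design effect 2 (effective m = 500).

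c = 1 + (1.96 + 0.84)² × [p0(1−p0)/m + p1(1−p1)/m + k²(p0² + p1²)] / (p0−p1)²

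The bracket is 0.00042 + 0.00049 + 0.01665 = 0.01756, and (p0−p1)² = 0.0144. This gives c = 10.57, so 11 per arm, with power 81.7%. The stated figure is reproduced, and the same k and design effect are used below.

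**Awareness subgroup, with no effect on behaviour.** Let a0 and a1 be awareness among HIV-positive people in control and intervention cities, rA the risk in those aware in either arm, and rN the risk in those aware only because of ICCs. These values are assumptions; the documents do not give them.

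- Control aware group: rA
- Intervention aware group: [a0·rA + (a1−a0)·rN] / a1
- Spurious difference: (a1−a0)/a1 × (rN−rA)

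With rA = 20%:

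| a0 → a1 | rN = 30% | rN = 40% |
|---|---|---|
| 30% → 40% | +2.5 points | +5.0 points |
| 30% → 50% | +4.0 points | +8.0 points |
| 40% → 50% | +2.0 points | +4.0 points |
| 40% → 60% | +3.3 points | +6.7 points |

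For example, (0.3×0.20 + 0.2×0.40)/0.5 = 0.28, against 0.20 in control. If the still unaware also have risk 40%, all HIV-positive people together show 0.3×0.20 + 0.2×0.40 + 0.5×0.40 = 34% in both arms, so the difference comes only from the split.

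The sign follows rN−rA. Exchanging the two risks gives (0.3×0.40 + 0.2×0.20)/0.5 = 0.32 against 0.40, or −8 points. If a1 = a0 or rN = rA, the difference is zero.

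**Chance of a nominally significant result.** A simulation used 11 vs 11 clusters, k = 0.25, 150 HIV-positive people per cluster (effective 75) and a t-test on log proportions, with 20,000 runs per setting. There was no adjustment for pre-intervention levels, so the rates are indicative.

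| Awareness | rA, rN | Aware subgroup, control vs intervention | Ratio | p < 0.05 |
|---|---|---|---|---|
| 30% → 44% | 30%, 50% | 30.0% vs 36.4% | 1.21 | about 20% |
| 30% → 50% | 20%, 40% | 20.0% vs 28.0% | 1.40 | about 43% |

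Starting awareness was 20% or 30% in these runs. Over all settings with a shift and a risk difference, ratios ran from 1.10 to 1.50 and false-positive rates from 9% to 53%. With no shift or no risk difference, the ratio was 1.00 and the rate about 5%.

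**Substance-use subgroup, with no effect on HIV testing.** Assume use of 40% in control and 30% in intervention cities, and testing of 25% in continuing users and 35-45% in those who stop because of ICCs. Users in control cities then show (0.3×0.25 + 0.1×0.45)/0.4 = 30.0%, or 27.5% with 35% in place of 45%. Users in intervention cities show 25%. The ratios are 0.83 and 0.91, with false-positive rates of 30% and 12%.

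**The case against.** The plan never says that arms will be compared by awareness; it says only that subgroup analyses are planned. That is so, but the sentence closes a paragraph on community-level comparisons, and for substance use the plan does speak of comparing outcomes within subgroups. The arm contrast is the natural reading, though for awareness it remains an inference. Likewise, a reader might take the factor to be current substance use. The text gives no window; post-intervention measurement follows from the design.

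A reader might also infer that the test of hypothesis 3 is compromised. The documents do not support this. Hypothesis 3 concerns MSM and PWID as a whole. Its behavioural outcomes in Table 1 use participants at MSM or PWID sites (for outcome 14, active injectors), without splitting by awareness. The planned full-sample comparisons are not affected.

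The magnitude is wholly assumed. No document gives risk by time since diagnosis, and neither the direction nor the presence of bias can be known in advance. The shift in awareness is the trial's own hypothesis; the difference in risk is plausible but undocumented. This limits the claim to what can happen.

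Finally, part of the remedy is already planned: serostatus subgroups are in the same sentence, and exploratory comparisons of people linked across surveys appear under Network- and individual-levels. Neither is wholly clean. Serostatus could shift slightly if incidence falls, and linked people are selected after randomisation. Both points stand and shape the fix.

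**Conclusion.** The concern holds for these subgroup analyses only. As written, the plan leads to arm contrasts within groups defined by factors that are themselves intended effects and trial outcomes, measured mainly after the intervention, with no caveat. Under the assumptions shown, the aware subgroup can differ by +2.0 to +8 points with no effect on behaviour. That range depends on the newly aware having 10 to 20 points higher risk than the already aware. The documents do not support saying that a false effect will appear, or that it would run in a given direction. The issue is worth correcting because the remedy is cheap, but it does not threaten the trial's main conclusions.

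**What to change.** Amend the subgroup paragraph of the Analysis plan as follows.

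1. State that results by awareness or substance use measured at the post-intervention survey are descriptive and do not estimate an intervention effect.
2. For risk behaviours and the other listed outcomes in HIV-positive people, rely on the planned comparison among all seropositive participants regardless of awareness. Note that serostatus could itself shift slightly through incidence.
3. For effect modification, use the city's pre-intervention level of awareness or substance use. City-level awareness was already available for the restricted randomisation (Table 3), and substance use is a survey module (Table 2).
4. As an exploratory addition, use the person's own pre-intervention value among participants linked by fingerprint, stating that this subset is smaller and selected after randomisation.

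The cost is wording; no new data are needed. What is lost is detail: city-level modifiers are coarse with 22 cities, and the linked subset is less precise.

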- 820 68. Laeyendecker O, Kulich M, Donnell D, Komarek A, Omelka M, Mullis CE et al. Development of
821 methods for cross-sectional HIV incidence estimation in a large, community randomized trial. *PLoS One*.
822 2013;8(11):e78818.
823
- 824 69. Hemelaar J, Gouws E, Ghys PD, Osmanov S, Isolation W-UNfH, Characterisation. Global trends in
825 molecular epidemiology of HIV-1 during 2000-2007. *AIDS*. 2011;25(5):679-89.
826

827

828

829 **Figure 1. Study Design**

830 Abbreviations: MSM, Men who have sex with men; PWID, People who inject drugs; RDS,

831 Respondent-driven sampling; ICC, Integrated care centers

832

833 **Figure 2. Study Sites. Panel A.** MSM sites represent cities with established HIV epidemics
834 among MSM (Chennai, Hyderabad, Bengaluru), smaller cities in high HIV prevalence states
835 (Coimbatore, Madurai, Vishakapatnam, Vijaywada, Mangalore, Belgaum) and cities with
836 anecdotal reports of HIV among MSM but no published reports (New Delhi, Bhopal, Lucknow).

837 **Panel B.** PWID sites represent cities with established drug use epidemics (Aizawl,
838 Churhandpur, Dimapur, Gangtok, Imphal, Lunglei, Moreh), large cities (New Delhi, Mumbai)
839 cities with documented emerging drug use epidemics (Amritsar, Chandigarh, Ludhiana) and
840 cities with anecdotal evidence of emerging drug use epidemics (Bilaspur, Bhubaneswar,
841 Kanpur). Note New Delhi has two control sites (one for the MSM stratum and one for the PWID
842 stratum).

843

844

845 **Supplementary files**

846

847 File name: MSM Baseline Survey

848 Title of data: MSM Baseline Survey

849 This survey was distributed (in local languages) to MSM study sites to gather baseline data on
850 HIV status and risk behaviors.

851

852 File name: PWID Baseline Survey

853 Title of data: PWID Baseline Survey

854 This survey was distributed (in local languages) to PWID study sites to gather baseline data on
855 HIV status and risk behaviors.

Table 1. Outcome definitions for the Indian National Collaboration on AIDS (NCA) study

	Outcome	Data inputs	Population (denominator)	Definition
Primary Outcome				
HIV testing				
1	HIV testing in the prior 12 months	Survey	All participants, excluding those that report being HIV-positive AND report being tested more than 12 months ago.	Either 1 OR 2: 1. Reports HIV test within the prior 12 months OR 2. Was told he/she had HIV within the last 12 months
Secondary Outcomes				
Awareness of HIV status, access to care, and HIV treatment				
2	Awareness of HIV status among HIV-seropositive persons	1. Survey 2. Serologic HIV test	HIV seropositive participants	Reports having a positive HIV test OR being told by a doctor that he/she had HIV.
3	Accessing HIV medical care in prior 6 months	1. Survey 2. Serologic HIV test	HIV seropositive participants	Reports seeing a doctor about HIV AND reports visit with the indicated doctor in the prior 6 months.
4	Use of ART among ART-eligible	1. Survey 2. Serologic HIV test	HIV seropositive participants who meet either criteria 1 or 2 1. Reports taking ART at any time in the past OR 2. CD4 <350 cells/ μ L	Reports ART use in prior 30 days.
5	Use of trimethoprim-sulfamethoxazole (TMP-SMX) when indicated	1. Survey 2. Serologic HIV test 3. CD4	HIV seropositive AND CD4 count < 200 cells/ μ L	Reports taking TMP-SMX in past 30 days
6	Viral suppression among ART-eligible	1. Survey 2. Serologic HIV test 3. CD4 4. HIV RNA	HIV seropositive participants who meet either criteria 1 or 2 1. Reports taking ART at any time in the past OR 2. CD4 <350 cells/ μ L	HIV RNA <150c/mL
7	Viral suppression among HIV-positive	1. Serologic HIV test 2. HIV RNA	HIV seropositive participants	HIV RNA <150c/mL
8	Average CD4 cell count among HIV-positive	1. Serologic HIV test 2. CD4 cell count	HIV seropositive participants	CD4 cell count

Table 1. Outcome definitions for the Indian National Collaboration on AIDS (NCA) study

	Outcome	Data inputs	Population (denominator)	Definition
Risk behaviors, substance use, and depression				
9	Unprotected anal intercourse with non-main male partner in prior 6 months [MSM]	Survey	Participants at MSM sites	Does not report “always” using a condom during insertive or receptive anal sex with non-main (e.g., casual, one-time partner, sex worker) male partners in the prior 6 months
10	Number of non-main male sexual partners in prior 6 months [MSM]	Survey	Participants at MSM sites	Number of non-main male (e.g., casual, one-time partner, sex worker) male partners with whom the participant reports having insertive or receptive anal sex in the prior 6 months
11	Symptoms of sexually transmitted infection [MSM]	Survey	Participants at MSM sites	Reports genital/anal discharge, pain, or ulcer in prior 6 months
12	Syphilis infection	1. RPR test 2. TPHA test	Participants at MSM sites	Positive for syphilis infection by both RPR and TPHA tests
13	Shared injection equipment in prior 6 months [PWID]	Survey	Participants at PWID sites	Reports sharing (passing or receiving) a needle and/or syringe with another individual in the prior 6 months
14	Shared injection equipment at last use among active injectors [PWID]	Survey	Participants at PWID sites that report injection of one or more drugs in prior 6 months	Reports sharing (passing or receiving) a needle and/or syringe with another individual at last injection
15	Reported injection abstinence in prior 6 months [PWID]	Survey	Participants at PWID sites	Denies injecting any drug in prior 6 months
16	Hazardous alcohol use or dependence	Survey	All participants	Score ≥ 8 (hazardous) or ≥ 15 on Alcohol Use Disorder Identification Test (AUDIT)[61]
17	Depression	Survey	All participants	Score ≥ 10 on Patient Health Questionnaire (PHQ)-9[62]

Table 1. Outcome definitions for the Indian National Collaboration on AIDS (NCA) study

	Outcome	Data inputs	Population (denominator)	Definition
Services and stigma				
18	Spouse HIV testing among married participants	Survey	Participants who report being married	Reports spouse has ever been tested for HIV
19	Symptoms of sexually transmitted infection for which participant sought care in prior 6 months [MSM]	Survey	Participants at MSM sites	Reports genital/anal discharge, pain, or ulcer in prior 6 months AND reports seeking medical care for symptom(s)
20	Used needle/syringe exchange program (NSEP) in prior 6 months [PWID]	Survey	Participants at PWID sites	Reports NSEP use in prior 6 months
21	Used needle/syringe exchange program (NSEP) in prior 6 months among active injectors [PWID]	Survey	Participants at PWID sites that report injection of one or more drugs in prior 6 months	Reports NSEP use in prior 6 months
22	Used opioid agonist therapy (OAT) in prior 6 months [PWID]	Survey	Participants at PWID sites	Reports OAT in prior 6 months
23	Stigma subtypes	Survey	All participants	Summed score from each of four 6-item stigma scales (enacted, vicarious, felt normative, and internalized stigma)[63]
Community viral load and HIV incidence				
24	Prevalence of viremic individuals in population	1. Serologic HIV test 2. HIV RNA	All participants	Prevalence of HIV-positive subjects with HIV RNA >150c/mL[64]
25	Average viral load in HIV-positive participants	1. Serologic HIV test 2. HIV RNA	HIV seropositive participants	Average (log ₁₀) HIV RNA
26	HIV incidence	1. Serologic HIV test 2. HIV RNA 3. CD4 cell count 4. BED assay 5. Avidity index	Participants who meet criteria 1 or 2 1) HIV-seronegative OR 2) HIV-seropositive participants who meet criteria for recent infection by HIV RNA, CD4, BED assay, and avidity assay	Cross-sectional HIV incidence estimated as described previously[64, 7, 6]

Table 2. Data Collection

	MSM	PWID
Survey modules		
Demographics	X	X
Peer network size	X	X
HIV testing, care and medications (HIV care continuum)	X	X
HIV treatment knowledge (including questions on other local HIV testing and treatment efforts)	X	X
Substance use (drugs, alcohol), injection-related risk behavior, sexual risk behavior	X	X
Service utilization (NSEP, OST, condom provision)	X	X
Tuberculosis history	X	X
Depressive symptoms (Patient Health Questionnaire-9 [65, 62])	X	X
Social support	X	X
Stigma (Enacted, vicarious, felt normative, internalized MSM stigma)	X	
Stigma (Enacted, vicarious, felt normative, internalized PWID stigma)		X
Quality of life (adapted version of EuroQOL [66])	X	X
Acceptability of novel prevention interventions (early ART, circumcision, PrEP)	X	X
Sexual health (including STI history)	X	
Hepatitis C virus and Hepatitis B virus testing, care and treatment		X
Laboratory testing		
HIV ⁸		
Determine HIV 1/2, Alere Medical Co., Ltd., Chiba, Japan	X	X
First Response HIV Card Test 1-2.0, PMC Medical India Pvt, Ltd, Daman, India		
Signal Flow Through HIV 1+2 Spot/Immunodot Test kit, Span Diagnostics Ltd, Surat, India		
CD4 count*	X	X
Flow cytometry, Epics XL – MCL, Beckman Coulter Inc., USA		
HIV RNA*	X	X
RealTime HIV-1 Assay, Abbott Laboratories, Abbott Park, Illinois, USA		
BED assay*	X	X
Aware TM BED TM EIA HIV-1 Incidence Test (IgG Capture HIV-EIA), Calypte Biomedical Corporation, Portland, OR, USA		
Avidity[67]*	X	X
GS HIV-1/HIV-2 PLUS O EIA, Biorad Laboratories, Redmond, USA using diethyl amine as the chaotropic agent		
HSV-2	X	
Anti-HSV-2 (gG2) ELISA (IgG), Euroimmun Medizinische Labordiagnostika AG, Lubeck, Germany		
Syphilis	X	
RPR Test Kit, Span Diagnostics Ltd. Surat, India		
Immunotrep TPHA, Omega Diagnostics Limited, Scotland, UK		

Abbreviations: NSEP, Needle and syringe exchange programs ; OST, Opioid substitution therapy ;MSM, Men who have sex with men; PWID, People who inject drugs; ART, Antiretroviral therapy; PrEP, Pre-exposure prophylaxis; STI, Sexually transmitted infections

*Tests performed only among those who tested HIV positive. Cross-sectional estimation of HIV incidence was based on a multi-assay algorithm (MAA) validated for HIV Subtype C[68] – the predominant subtype in India that included CD4, HIV RNA, BED and Avidity.[69]

Table 3. Description of Stratum-specific and Overall Restriction Criteria

	Stratum-specific		Overall
	MSM	PWID	
GEOGRAPHICAL RESTRICTIONS			
Tamil Nadu (3)	3 sites distributed at a ratio of 2:1 (Madurai/Chennai in separate arms)		
Andhra Pradesh (3)	3 sites distributed at a ratio of 2:1		
Karnataka (2), Bhopal, Delhi	4 sites distributed with at least one site in each arm		
Northeast (5)		5 sites distributed at a ratio of 3:2	
North (4)		4 sites distributed at a ratio of 2:2	
West/Central India (3)		3 sites distributed at a ratio of 2:1	
RESTRICTIONS BASED ON OUTCOMES			
HIV prevalence	< 1.5% ^a	< 2% ^a	< 2% ^c
Percentage who had HIV test in the prior 12 months [PRIMARY OUTCOME]	< 5% ^a	< 5% ^a	< 5% ^c
Percentage of HIV positive aware of status	< 10% ^{a,b}	< 10% ^{a,b}	< 10% ^c
Percentage of HIV positive seen HIV provider in past 6 months	< 10% ^{a,b}	< 10% ^{a,b}	< 10% ^c
Percentage of HIV positive currently on antiretroviral therapy	< 10% ^{a,b}	< 10% ^{a,b}	< 10% ^c
Percentage of HIV positive with undetectable HIV RNA	< 9% ^a	< 9% ^a	< 9% ^c

^aRestrictions placed on only RDS-weighted proportions; RDS-I estimator used for PREVALENCE and TEST; RDS-II estimator used for other outcomes because RDS-I estimator could not be calculated

^bRestriction was across three outcomes (Proportion of HIV positive aware of status, Proportion of HIV positive seen HIV provider in past 6 months, Proportion of HIV positive currently on antiretroviral therapy); Only those with values >10% in 2 of the three outcomes were excluded

^cRestrictions placed on RDS-weighted and unweighted proportions
